#### **Baseline number of positive cores**

Maximum number of positive cores in the left lobe across both biopsies + maximum number of positive cores in the right lobe across both biopsies.

#### **Baseline maximum cancer core length**

Maximum cancer core length in the left lobe across both biopsies + maximum cancer core length in the right lobe across both biopsies.

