5.2 Inclusion Criteria

Subjects will be eligible for inclusion in the study if all of the following criteria are met:

1. Men over 18 years of age;
2. Patients who have had a multiparametric MRI of the prostate performed and have undergone transrectal systematic biopsy plus biopsy of any volumes considered suspicious per the MRI (PIRADS version 2 score of 4 or 5) within 6 months before signing consent;
3. Histological diagnosis of prostate cancer identifying Gleason score of 3+4 on one half of the prostate gland (right or left) in no more than 2 sextants of the prostate gland and not present in more than 50% of any one core taken systematically. The involvement criterion does not apply to cores taken from MRI suspicious volumes;
4. Patients with concomitant Gleason score 3+3 prostate cancer in less than 50% of any core at any site will be considered eligible;
5. Prostate cancer stage up to cT2a – N0/Nx – M0/Mx;
6. Prostate volume ≥ 25 mL and ≤ 70 mL;
7. Serum PSA ≤ 10 ng/mL;

8. Men who are sexually active with women of childbearing potential must use contraceptive method with a failure rate of less than 1% per year. Contraception should be continued for a period of 90 days after the VTP procedure. The individual methods of contraception may be determined in consultation with the investigator;
9. Signed Informed Consent Form.

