6 TREATMENT OF SUBJECTS

6.1 Entry into study

6.1.1 Entry Biopsy

Only patients with at least one prior prostate biopsy will be considered. Additionally:

- The biopsy must demonstrate any Gleason score 7 (3+4) prostate adenocarcinoma in 1 or 2 sextants on one side of the prostate gland.
- The biopsy must include a minimum of 12 cores and must have at least 1 core from each prostate sextant.
- All cores from the prior biopsy must have been evaluated and results confirmed at the treating institution.
- Standard definition for prostate sextant anatomy will be used: Right and Left; Apex, Mid and Base. Transition zone biopsies, if present, will be considered as Mid gland.
- Targeted biopsy of suspicious lesions seen on MRI that meet PIRADS (version 2) criteria for level 4 or 5 lesions will be required before patients may be considered eligible.
- Patients who meet initial biopsy eligibility criteria with PIRADS (version 2) criteria lesions of level 3 or less will not require targeted biopsy.
- If a patient has undergone biopsy without MRI and subsequently undergoes MRI but no suspicious (PIRADS 4 or 5) lesions are observed, additional biopsy is not needed for inclusion.

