6.2.3 Treatment Conditions

Treatment guidance will help to determine the number and position of laser fibers to be inserted, with the length of illumination necessary to achieve a Light Density Index ≥ 1 in the targeted tissue. In case of unilateral disease, focal treatment of one lobe will be applied. In case of bilateral disease (discovered at entry or during follow-up), bilateral treatment will be applied consecutively or simultaneously. Retreatment of lobes found positive for cancer at 3-months follow-up will be allowed, provided there is no sign of cancer progression in the treated lobe and the patient did not experience grade 3 or 4 adverse events.

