7 OUTCOMES ASCERTAINMENT

7.1 Prostate biopsy

All subjects will undergo biopsy at 3 and 12 months according to protocol. The need for subsequent biopsy beyond 12 months will be at the discretion of the investigator according to standard of care. All biopsy procedures will consist of a transrectal ultrasound guided prostate biopsy with a minimum of 12 cores and include both lobes of the prostate gland. Any suspicious volumes meeting PIRADS (version 2) criteria of level 4 or 5 found on MRI will be targeted with at least 2 cores taken from each suspicious lesion. Patients will undergo pre-biopsy preparation using standard of care practices for the institution that should include the use of peri-procedural antibiotics. Patients who fail to receive antibiotics for the biopsy procedure will be considered a violation.

Anatomopathological reports will include:

1. The number and length of cores taken,

2. The number and the location of cores with cancer,
3. The cancer core length (CCL) which is linear millimeters of cancer on each core and the percentage of cancer on each core,
4. The Gleason grading of each core.

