#### **Baseline value**

Baseline value will be defined as the last reported value until the date of treatment.

For those patients with two biopsies at baseline the following definitions of baseline values will be applied:

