#### **Baseline total cancer core length**

Maximum total cancer core length in the left lobe across both biopsies + maximum total cancer core length in the right lobe across both biopsies.

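### For men with two baseline biopsies, the SAP derives baseline 'maximum' cancer core length by adding the two lobe maxima, which exceeds the longest cancer core whenever both lobes contain cancer

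*SAP*

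**What the plan says.** Under Baseline value, the SAP sets a general rule: "Baseline value will be defined as the last reported value until the date of treatment". It then makes an exception: "For those patients with two biopsies at baseline the following definitions of baseline values will be applied". Three definitions follow, for the number of positive cores, maximum cancer core length and total cancer core length.

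All three share one template: a left-lobe quantity plus a right-lobe quantity, each taken across both biopsies. For the maximum, the definition is "Maximum cancer core length in the left lobe across both biopsies + maximum cancer core length in the right lobe across both biopsies". For the total, it is "Maximum total cancer core length in the left lobe across both biopsies + maximum total cancer core length in the right lobe across both biopsies".

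Protocol section 7.1 lists what the pathology report must contain, including "The cancer core length (CCL) which is linear millimeters of cancer on each core and the percentage of cancer on each core". That fixes the unit: a length in millimetres belonging to a single core.

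The protocol allows cancer in both lobes at entry. Section 5.2 states "Patients with concomitant Gleason score 3+3 prostate cancer in less than 50% of any core at any site will be considered eligible", and section 6.2.3 provides for it: "In case of bilateral disease (discovered at entry or during follow-up), bilateral treatment will be applied consecutively or simultaneously". It also leaves room for two baseline biopsies. Section 6.1.1 says "Targeted biopsy of suspicious lesions seen on MRI that meet PIRADS (version 2) criteria for level 4 or 5 lesions will be required" before a man can be considered eligible, and such a biopsy may follow an earlier systematic one.

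**The concern.** Adding the lobes is coherent for a count of positive cores and for a total length, because both quantities add across the gland. A maximum does not. The sum of the longest cancer core on the left and the longest on the right is not the length of cancer in any core the man had, yet the SAP labels it a maximum. It looks as though the template for the count and the total was carried over to a quantity it does not fit. The SAP offers no reason for a sum of lobe maxima, and nothing elsewhere in either document corrects it.

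A programmer who follows the definition exactly will produce a mislabelled number. If the variable is tabulated, the longest cancer core at entry will be overstated in men who have both two baseline biopsies and cancer in both lobes.

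**Working it through.** The plan states no figure for this variable, so there is nothing to reproduce. The check compares the SAP rule with the quantity its label describes.

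**Inputs.** Let L and R be the longest cancer core length in the left and right lobe, each taken across both baseline biopsies. The rule and its scope come from the SAP (Baseline value; Baseline maximum cancer core length). The per-core unit comes from protocol section 7.1. The documents give no core lengths, so every millimetre value below is an assumption for illustration.

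**Formulas.**
- SAP rule: L + R.
- Longest cancer core: max(L, R).
- Overstatement: (L + R) − max(L, R) = min(L, R), the smaller lobe's maximum.
- Ratio: (L + R) / max(L, R) = 1 + min(L, R) / max(L, R). This is 1 when one lobe is free of cancer, above 1 when both lobes contain cancer, and 2 when the lobes are equal.

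**Illustrations.**

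| Assumed case | SAP rule (mm) | Longest cancer core (mm) | Ratio |
|---|---|---|---|
| L = 6, R = 0 | 6 | 6 | 1.00 |
| L = 6, R = 4 | 10 | 6 | 1.67 |
| First biopsy L = 6, R = 0; second biopsy L = 0, R = 4 | 10 | 6 | 1.67 |
| L = 6, R = 6 | 12 | 6 | 2.00 |

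The third row shows that the two lobes need not be positive at the same biopsy.

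**Can the value exceed a whole core?** Assume cores of 15 mm.
- Systematic cores only: section 5.2 allows Gleason 3+4 in at most 50% of a core and 3+3 in less than 50%. Taking 50% and 49% gives 7.5 + 7.35 = 14.85 mm, just under one core. The longest cancer core is 7.5 mm, so the ratio is 1.98.
- With a targeted core: section 5.2 exempts cores from MRI-suspicious volumes from the 3+4 limit. A targeted core at 80% (12 mm) plus an opposite-lobe core at 45% (6.75 mm) gives 18.75 mm, longer than any core taken. The longest cancer core is 12 mm, so the ratio is 1.56.

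**Where the variable is used.** The SAP's Demographic and baseline characteristics section names time since diagnosis, TNM staging, PSA, prostate volume, unilateral or bilateral disease, and total positive cores. Maximum cancer core length is not named, but the list is introduced as examples. Protocol section 10.2.2.1 mentions only the number of cores involved. The primary efficacy analysis, the secondary biopsy analyses, the analysis of additional therapy and the safety analyses do not refer to it.

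**The case against.** The strongest case on the other side is that nothing of consequence depends on this variable. No named analysis or table uses it, so an error in its definition may never reach a report. That stands as to importance. It does not remove the defect: the SAP pre-specifies the derivation, and the open list of baseline characteristics leaves room for it to be tabulated.

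A second argument is that a sum of lobe maxima is a usable index of burden, and only its name is wrong. That is also fair. The documents do not show which was intended, so renaming is an acceptable repair.

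A reader might go further in two directions that the documents do not support.

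- *That many men are affected, because targeted biopsy is required for PIRADS 4 or 5 lesions.* The error needs both two baseline biopsies and cancer in both lobes, and the documents give no frequency for either. Section 5.2 confines Gleason 3+4 to one half of the gland, so cancer in the other half comes in through the permitted 3+3. Systematic and targeted sampling can be done in one session. Section 6.1.1 waives targeted biopsy for lesions of PIRADS 3 or less, and waives a further biopsy when a later MRI shows no PIRADS 4 or 5 lesion. Two biopsies can occur; how often is unknown.
- *That a man with one biopsy gets a true maximum, so the variable is known to mix two quantities.* The SAP gives such men only the last-value rule and never says how a maximum is formed from one biopsy. A programmer could equally add the lobes, as the SAP does for total positive cores during follow-up. The derivation is undefined, not known to differ.

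**Conclusion.** The definition is wrong as written, at the lowest level of severity. Followed exactly, it overstates the longest cancer core by the smaller lobe's maximum in every man with two baseline biopsies and cancer in both lobes. The ratio is above 1 and at most 2. These bounds are algebraic and hold for any core lengths; only the millimetre examples rest on assumed values.

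Men with unilateral disease are unaffected, and the number of affected men cannot be estimated from the documents. The omission of a single-biopsy derivation is a related gap that leaves comparability between men unsettled. The primary result, the sample size of 44 and the success rule are untouched.

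**What to change.** In the SAP, under Baseline maximum cancer core length, define the variable as the larger of the left-lobe and right-lobe maxima across all baseline biopsies. State that this applies to every man, whether he had one biopsy or two. If a sum was intended, rename the variable 'sum of lobe maxima' and apply that definition to all men. The definitions for the number of positive cores and total cancer core length can keep their addition across lobes.

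The cost is a line or two of SAP text and one derivation in the analysis program. For men with two biopsies the corrected rule uses the same two lobe maxima as the present one, so no new data are needed. For men with one biopsy it uses the per-core lengths from that biopsy.

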#### **Baseline total cancer core length**

Maximum total cancer core length in the left lobe across both biopsies + maximum total cancer core length in the right lobe across both biopsies.

***Handling of missing data and/or invalid data and outliers*****IIEF questionnaire**

Subscale scores with at least 1 but not more than 50% missing items will be imputed using the formula:  $S = s \times T \div t$  where s is the observed score, S is the imputed score, T is the maximum total score for the subscale and t is the maximum score possible from the completed questions. Missing subscale scores will be imputed using a multiple imputation method (Markov Chain Monte Carlo method).

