5.5.3 Exit from the Study

Subjects will have the right to withdraw from participation in the study at any time, for any reason.

Subjects may be withdrawn from the study at the discretion of the Investigator only if continuation will jeopardise the subjects’ health and/or welfare. Every effort must be made to follow withdrawn subjects for safety reasons using the appropriate CRFs until the planned end of the study period.

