5.5.4 Subject withdrawal

The criteria for terminating participation in the study are detailed below:

1. Serious adverse event that is study-related (see definition further below), as recommended by the Investigator, patients with grade 3 or 4 adverse events following their initial treatment who have evidence of treatable prostate cancer on month 3 biopsy will not undergo re-treatment, will be withdrawn from the study and proceed with standard of care unless justification for continuing on study is specifically sought and approved from the IRB.
2. Subject withdrawal: at any time, a subject can withdraw from the study at his request or on the basis of the Investigator's clinical judgment.
3. Patients with evidence of clinical deterioration on the same side such as Gleason grade 5 cancer, more than 2 sextants including Gleason grade 4 cancer on the treated side on the 3-month re-biopsy will be withdrawn from the study and proceed with standard care.
4. Major protocol violation, defined as any violation that may impact the safety of a study subject.
5. Termination of the study by the Sponsor.

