7.2 Patients' questionnaires on erectile dysfunction and urinary symptoms

The following questionnaires will be applied to all patients to assess erectile function and urinary symptoms at entry and at months 1, 3, 6, 12, 24, 36, 48 and 60:

- IIEF-15 for erectile function

The International Index of Erectile Function (IIEF) relates to the following areas: confidence in erection; erection sufficient for penetration; maintaining of erection; difficulty to maintain erection for completion; satisfactory intercourse. Subjects will be asked to give their response to each of the areas using a 6-point scale (0=no sexuality, 5=best response).

- IPSS for lower urinary tract symptoms

The International Prostate Symptom Score (IPSS) is an 8-question questionnaire focused on urinary symptoms with one general question about urinary symptoms. The questions relate to the following areas: sensation of bladder emptying; frequency of urination; stops when urinating; difficulties to postpone urination; urinary steam; beginning of urination; night urination. Subjects will be asked to give their response to each of the areas using a 6-point scale (0=none or normal, 5=worse response).

These questionnaires will encompass the consequences of all treatments, including additional radical therapy potentially used by patients. Scores for each one of the scales will be calculated regardless of failure or not, and additional treatment or not.

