**IPSS questionnaire**

Scores with at least 1 but not more than 50% missing items will be imputed using the formula:  $S = s \times T \div t$  where s is the observed score, S is the imputed score, T is the maximum total score for the IPSS and t is the maximum score possible from the completed questions. Missing total scores will be imputed using a multiple imputation method (Markov Chain Monte Carlo method).

Other missing data, including biopsy data, will not be replaced.

A subject with missing Month 12 biopsy will be counted as failure for the primary analysis.

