#### **Safety analysis**

All safety analyses will be based on the safety population. A secondary analysis will include only those patients receiving retreatment at 3 months. Results will be tabulated.

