**IIEF (International Index of Erectile Function) questionnaire**

All items will be scored in 5 domains as follows:

- Erectile Function: sum of items 1, 2, 3, 4, 5 and 15 (score range: 1-30).
- Orgasmic Function: sum of items 9 and 10 (score range: 0-10).
- Sexual Desire: sum of items 11 and 12 (score range: 2-10).
- Intercourse Satisfaction: sum of items 6, 7 and 8 (score range: 0-15).
- Overall Satisfaction: sum of items 13 and 14 (score range: 2-10).

Descriptive summaries of the change from baseline will be provided for both Observed Cases and a multiple imputation method approaches.

In addition the erectile function score will be dichotomized as 22 or above vs. 21 and below and the proportion of cases with new onset erectile dysfunction at each timepoint (i.e. baseline score  $\geq 22$  but follow-up score  $< 22$ ) will be reported. For a secondary analysis, new onset erectile dysfunction will be described as baseline score  $\geq 22$ , follow-up score  $< 22$  and change from baseline of more than 2 points.

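### Neither document secures IIEF and IPSS scores after Month 3 withdrawal or specifies how to impute them, so reported function may look better than the all-treatments result the protocol asks for

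*SAP*

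**What the plan says.** **What the scores should cover.** Protocol 7.2: "These questionnaires will encompass the consequences of all treatments, including additional radical therapy potentially used by patients", and "Scores for each one of the scales will be calculated regardless of failure or not, and additional treatment or not". The forms are due at entry and at Months 1, 3, 6, 12, 24, 36, 48 and 60.

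**Who leaves.** Protocol 4.1 withdraws men with same-side deterioration at Month 3 to standard care. It does the same for men with treatment-related grade 3–4 events and cancer on the Month 3 biopsy, unless the IRB approves continuing. Section 5.5.4 describes the first group differently, as Gleason grade 5 or the following: "more than 2 sextants including Gleason grade 4 cancer on the treated side on the 3-month re-biopsy will be withdrawn from the study and proceed" (to standard care). The synopsis extends the IRB exception to both groups.

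**What is collected afterwards.** Protocol 5.5.3: "Every effort must be made to follow withdrawn subjects for safety reasons using the appropriate CRFs until the planned end of the study period". The questionnaires are not named.

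**How missing scores are handled.** For the IIEF, the SAP says "Missing subscale scores will be imputed using a multiple imputation method (Markov Chain Monte Carlo method"; for the IPSS, "Missing total scores will be imputed using a multiple imputation method (Markov Chain Monte Carlo method". No imputation variables are listed. The IIEF section says "Descriptive summaries of the change from baseline will be provided for both Observed Cases and a multiple imputation method approaches", and the IPSS section has a matching statement. Both sections follow the SAP heading Safety analysis, where "All safety analyses will be based on the safety population". The IIEF section also defines a proportion with new-onset erectile dysfunction (baseline erectile score of 22 or more, follow-up below 22) and says nothing about imputing it. Under Statistical plan and methods, percentages rest on available observations unless stated otherwise.

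**The concern.** The protocol asks for function after VTP and whatever followed it. Men withdrawn at Month 3 leave because of treatment failure or toxicity, and some will go on to treatments with a heavier functional cost. If their later scores are missing, the missingness is tied to the outcome.

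Both planned summaries then lean the same way. Observed Cases leaves these men out. An imputation model without a therapy term fills their scores from the men with observed scores, who may mostly have had VTP alone. Agreement between the two would look like robustness when it is a shared blind spot.

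Preserved function is a main argument for VTP over radical treatment in protocol 2.1 and 2.2.4, and it is secondary objective 6. A favourable lean here bears on a claim that readers will care about.

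**Working it through.** The documents state no expected rate of missing questionnaires, of Month 3 withdrawal or of new-onset dysfunction after VTP. There is therefore no planned figure to reproduce, and what follows is illustrative.

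**Inputs**
- *r*, erectile dysfunction after radical therapy: 30–70% (protocol 2.1). This is dysfunction among treated patients, not the SAP's new onset among men with a baseline score of 22 or more.
- *v*, new-onset rate after VTP alone: not given; assumed 10%, 20% or 30%.
- *f*, share of men whose scores are missing after additional therapy: not given; assumed 3, 5 or 10 of 50 (6%, 10%, 20%). The same share is assumed among men with a baseline score of 22 or more.

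**Step 1: new-onset rate.** Suppose every man with an observed score had VTP alone. The reported rate is then v, and the all-treatments rate is (1 − f)v + fr. The understatement is

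f × (r − v).

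| f | r | v = 10% | v = 20% | v = 30% |
|---|---|---|---|---|
| 6% | 30% | 1.2 | 0.6 | 0.0 |
| 6% | 70% | 3.6 | 3.0 | 2.4 |
| 10% | 30% | 2.0 | 1.0 | 0.0 |
| 10% | 70% | 6.0 | 5.0 | 4.0 |
| 20% | 30% | 4.0 | 2.0 | 0.0 |
| 20% | 70% | 12.0 | 10.0 | 8.0 |

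(Percentage points. The largest is 0.20 × (0.70 − 0.10) = 0.12.)

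**Step 2: some men stay on study after additional therapy.** Protocol 6.4.11 allows radical therapy at any time. If a further share g has observed scores after such therapy, the observed rate is [(1 − f − g)v + gr] / (1 − f), which lies above v, so the gap narrows. With f = g = 10%, v = 10% and r = 50%:
- observed: (0.80 × 0.10 + 0.10 × 0.50) / 0.90 = 0.13 / 0.90 = 14.4%
- all treatments: 0.80 × 0.10 + 0.20 × 0.50 = 18.0%
- gap: 3.6 points, against 0.10 × (0.50 − 0.10) = 4.0 points when g = 0.

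**Step 3: would a therapy term in the imputation help?** A simulation used 50 men, 5 of them with additional therapy. It assumed a mean change of −2 points after VTP and a further 8-point loss after additional therapy. Imputation was by a normal model on baseline score, over 2,000 replicates. Mean change from baseline:

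| Post-therapy scores observed | Truth | Imputed, no therapy term | Imputed, therapy term |
|---|---|---|---|
| none | −2.8 | −2.0 | −2.0 |
| half | −2.8 | −2.4 | −2.8 |
| all | −2.8 | −2.8 | −2.8 |

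The term works only when some post-therapy scores exist. With none, the model has nothing to learn from. With all, there is no bias to remove. Collection therefore comes first. The simulation concerns the mean; the SAP reports medians and quartiles, and a small group usually moves the median less.

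**The case against.** The strongest reply is that nothing here need go wrong. The SAP's imputation rule is silent on additional therapy, and silence is not exclusion. The questionnaires sit under the safety analysis, in the safety population, and nobody is removed for additional therapy, so scores collected after it count as observed. Protocol 7.2 applies the forms to all patients. Section 5.5.3 asks for strenuous follow-up of withdrawn men to the planned end, and the SAP's placement of the scores under safety suggests that the questionnaires are included. The endpoint is descriptive with no test, and time to additional therapy is reported separately.

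Most of this stands, and it rules out stronger readings. A reader might infer that the SAP ignores additional therapy or breaks the protocol's rule. The documents show neither: they leave a gap. A reader might infer that withdrawn men are scored as VTP-only patients. Observed Cases leaves out men with missing scores rather than scoring them, and imputation would resemble VTP alone only if scores are missing, the model lacks a therapy term and the observed men mostly had VTP alone. A reader might also use the margin between 50 treated and 44 evaluable men as the share lost. The protocol does not tie that margin to Month 3 withdrawal, radical therapy or missing questionnaires, and it does not equate standard care with radical therapy.

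What does not stand is the assurance that 5.5.3 already secures the forms. Protocol 9 lists safety assessments as adverse events, anaesthetic monitoring and laboratory tests, and 10.4 places the questionnaires among the secondary efficacy endpoints. On the protocol's own terms, follow-up for safety need not include them.

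**Conclusion.** The concern holds as a conditional one. If scores after additional therapy are missing, Observed Cases, an imputation without a therapy term and the default new-onset proportion would all tend to show better function than the all-treatments result in protocol 7.2. Over the assumed ranges the new-onset rate is understated by 0 to 12 points. The direction depends on r exceeding v; the bias is zero where they are equal, and zero if the scores are collected. The size cannot be narrowed from the documents, because f and v are assumptions and r is a different measure from the SAP's endpoint. The two descriptions of same-side deterioration, in 4.1 and 5.5.4, also leave the number of withdrawn men open and must be reconciled. This affects a secondary, descriptive endpoint, not the primary analysis. It is worth correcting because the repair is cheap and uses forms and therapy records the trial already has.

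**What to change.** 1. **Protocol 5.5.3:** name the IIEF and IPSS among the forms collected to Month 60 from withdrawn men who agree. This comes first, because the later steps cannot replace scores that were never collected.
2. **SAP, missing-data rules for the IIEF and IPSS:** include in the imputation model a visit-specific indicator of additional prostate cancer therapy, as defined under Initiation of additional therapy.
3. **SAP, IIEF section:** report new-onset erectile dysfunction in the safety population with a sensitivity range. Among men with a baseline score of 22 or more, count those whose scores are missing after withdrawal or additional therapy first all as new onset, then none. Rely on this range where few or no post-therapy scores are observed.
4. **SAP, IIEF and IPSS sections:** label any summary that leaves these men out as doing so.

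The cost is a short protocol amendment, SAP wording, one more imputation variable and extra table rows. No extra patients or procedures are needed beyond existing questionnaires from men who agree. The functional result may look slightly less favourable, and the range can be wide. Its width is the number missing divided by the number with a baseline score of 22 or more: 5 missing of 50 gives 10 points and 10 of 50 gives 20, and more if fewer than 50 men start at 22 or above.
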